3.2. Subject Selection Criteria

3.2.1. Inclusion Criteria

Specific information regarding warnings, precautions, contraindications, adverse events (AEs), and other pertinent information on the GSK study treatment that may impact subject eligibility is provided in the Investigator Brochure (IB) for GSK2879552 [GlaxoSmithKline Document Number [2013N168888_03](#)]

Deviations from inclusion criteria are not allowed because they can potentially jeopardize the scientific integrity of the study, regulatory acceptability or subject safety. Therefore, adherence to the criteria as specified in the protocol is essential.

Subjects eligible for enrolment in the study must meet all of the following criteria:

1. ≥ 18 years of age and provided signed written informed consent.

2. Subjects must have relapsed/refractory acute myeloid leukemia by WHO classification for which no standard therapies are available or anticipated to result in a durable remission. FAB subtype M3 will be excluded.
3. Subjects ≥ 60 years of age with AML who are not candidates for or have refused standard chemotherapy.
4. Subjects who have previously received an autologous stem cell transplant are allowed if a minimum of 3 months has elapsed from the time of transplant and the subject has recovered from transplant-associated toxicities prior to the first dose of GSK2879552.
5. Subjects with a history of allogeneic stem cell transplant are eligible for study participation provided the following eligibility criteria are met:
 - transplant was >60 days prior to study enrollment.
 - subject has not taken immunosuppressive medications (including but not limited to: cyclosporine, tacrolimus, methotrexate, or mycophenolate mofetil) for at least 1 month
 - no signs or symptoms of graft versus host disease other than Grade 1 skin involvement
 - no active infection
6. Eastern Cooperative Oncology Group (ECOG) performance status of 0-1.
7. Subjects must be stable and, in the opinion of the investigator, be expected to complete 4 week treatment period.
8. Able to swallow and retain orally administered medication and does not have any clinically significant gastrointestinal abnormalities that may alter absorption such as malabsorption syndrome or major resection of the stomach or bowels,
9. All prior treatment-related toxicities must be National Cancer Institute- Common Toxicity Criteria for Adverse Events (NCI-CTCAE), version 4.0 \leq Grade 1 at the time of enrollment (except for alopecia).
10. Adequate baseline organ function defined by:

System	Laboratory Values
Hematologic	
White blood cell count (absolute)	≤30,000/uL
Coagulation assays (PT/INR and aPTT)	≤1.3 X ULN
Hepatic	
Total bilirubin	≤ 1.5 X ULN ¹
ALT and AST	≤2.5 × ULN
Renal	
Calculated creatinine clearance by Chronic Kidney Disease Epidemiology Collaboration (CKD-EPI) equation (Appendix 3) or measured from 24hr urine	≥ 40 mL/min
Cardiac	
Ejection fraction	≥ LLN by Echocardiogram (ECHO) or MUGA
Lipid (ATRA combination ONLY)	
Triglyceride (fasting)	≤ 300 mg/dL
Cholesterol (fasting)	≤ 300 mg/dL

1. Isolated bilirubin >1.5 X ULN is acceptable if bilirubin is fractionated and direct bilirubin <35% or subject has a diagnosis of Gilbert's syndrome

NOTE: Laboratory results obtained during Screening should be used to determine eligibility criteria. In situations where laboratory results are outside the permitted range, the investigator may opt to retest the subject and the subsequent within range screening result may be used to confirm eligibility.

11. Women of childbearing potential must have a negative serum pregnancy test within 7 days of first dose of study treatment and agree to use effective contraception (Section [11.1](#)), during the study and for 7 days (GSK2879552 mono therapy) or 30 days (combination with ATRA), following the last dose of study treatment.
12. Men with a female partner of childbearing potential must have either had a prior vasectomy or agree to use effective contraception (Section [11.1](#)) from the administration of the first dose of study treatment until 3 months after the last dose of study treatment to allow for clearance of any altered sperm.

3.2.2. Exclusion Criteria

Deviations from exclusion criteria are not allowed because they can potentially jeopardize the scientific integrity of the study, regulatory acceptability or subject safety. Therefore, adherence to the criteria as specified in the protocol is essential.

Subjects meeting any of the following criteria must not be enrolled in the study:

1. Active Human Immunodeficiency Virus (HIV), Hepatitis B Virus (HBV) or Hepatitis C Virus (HCV) infections at the time of screening. Subjects with laboratory evidence of HCV clearance (HCV RNA PCR is negative) may be enrolled.
2. History of or concurrent malignancy of solid tumours, except for below.

Exception: Subjects who have been disease-free for 5 years, or subjects with a history of completely resected non-melanoma skin cancer or successfully treated in situ carcinoma are eligible. Subjects with second malignancies that are indolent or definitively treated may be enrolled even if less than 5 years have elapsed since treatment. Consult GSK Medical Monitor if unsure whether second malignancies meet requirements specified above

3. Currently receiving cancer therapy (chemotherapy, radiation therapy, immunotherapy, biologic therapy, hormonal therapy, surgery, and/or tumour embolization)

Note: HYDREA (hydroxyurea) will be allowed.

4. Received major surgery, radiotherapy, or immunotherapy within 4 weeks of GSK2879552 administration.
5. Prior treatment with temozolomide, dacarbazine or procarbazine
6. Prior treatment with poly ADP ribose polymerase (PARP) inhibitors (e.g., olaparib, ABT-888)
7. Screening Montreal Cognitive Assessment (MOCA) score of 22 or lower
8. Evidence of severe or uncontrolled systemic diseases (e.g., severe/chronic infection, unstable or uncompensated respiratory, renal, or cardiac disease). Any serious and/or unstable pre-existing medical (aside from malignancy exception above), psychiatric disorder, or other conditions that could interfere with subject's safety, obtaining informed consent or compliance to the study procedures, in the opinion of the Investigator
9. Current active liver or biliary disease (with the exception of Gilbert's syndrome or asymptomatic gallstones, liver metastases or otherwise stable chronic liver disease per investigator's assessment).
10. Patients at risk of non-AML related major bleeding (e.g. recent GI hemorrhage or neurosurgery).
11. Symptomatic or untreated CNS leukemia. Subjects are permitted to enroll if previously treated for CNS disease, free of symptoms at the time of screening, and have not required intrathecal chemotherapy at least 1 month prior to study Day 1.
12. Cardiac abnormalities as evidenced by any of the following:
 - Clinically significant uncontrolled arrhythmias or uncontrolled hypertension.
 - History or evidence of current \geq Class II congestive heart failure as defined by New York Heart Association (NYHA, [Appendix 2](#)).
 - History of acute coronary syndromes (including unstable angina and myocardial infarction), coronary angioplasty, or stenting within the past 3 months.

- Baseline QTc interval using Fridericia's formula ≥ 450 msec or ≥ 480 msec in subjects with Bundle Branch Block. QTc value based on single or average of triplicate ECGs obtained over a brief recording period.
13. Administration of an investigational drug within 14 days or 5 half-lives, whichever is **shorter** with a minimum of 14 days preceding the first dose of study treatment(s) in this study.
 14. Have a known immediate or delayed hypersensitivity reaction or idiosyncrasy to drugs chemically related to GSK2879552 or LSD1 inhibitors that contraindicates their participation.
 15. Lactating female.
 16. Consumption of Seville oranges, grapefruit, grapefruit hybrids, grapefruit juice, pommelos, or exotic citrus fruits, from 1 day prior to the first dose of study treatment(s) until the last dose of study drug.
 17. Current use of a prohibited medication including anticoagulants or platelet inhibitors (Section 10.2) or expected to require any of these medications during treatment with the investigational drug.
 18. Previous treatment with GSK2879552

For ATRA Combination arm ONLY

19. Known hypersensitivity to ATRA, parabens (preservatives in the gelatin capsule) or other retinoids.
20. ATRA capsule contains sorbitol. Subjects with rare hereditary problems of fructose intolerance are excluded.
21. History of seizure within 12 months or brain tumor (primary)
22. History of taking mega-dose vitamin A ($>25,000$ USP U/day) within 3 months from the dosing start.

4. INVESTIGATIONAL PLAN

4.1. Discussion of Study Design

This is a Phase I, open-label, multi-center, non-randomized, 2-part study. Part 1 is a dose escalation phase to determine the MTD and/or RP2D for GSK2879552, alone or in combination with ATRA, based on the safety, tolerability, pharmacokinetic, and pharmacodynamic profiles observed after oral administration of GSK2879552. Eligible subjects with relapsed/refractory acute myeloid leukemia or elderly subjects who are ineligible for or refuse induction therapy will be enrolled. Any dose level(s) may be expanded up to 12 subjects in order to collect additional data on safety, tolerability, PK and PD.

[figure not shown]
Once MTD and/or RP2D is identified, an expansion cohort (Part 2) of up to 30 subjects each will be enrolled to further evaluate the efficacy and tolerability of GSK2879552, alone or in combination with ATRA, in subjects with relapsed/refractory AML.

The proposed treatment schedule of GSK2879552 is continuous daily dosing. The starting dose for GSK2879552 mono therapy arm will be 0.25 mg/day or the highest dose determined to be safe in the ongoing SCLC study, whichever is higher with a maximum of 1 mg/day (see Section 1.4.3.2 for details). The starting dose of GSK2879552 in combination with ATRA will be 1-2 dose levels below the highest dose determined to be safe in the GSK2879552 mono therapy arm in this study, i.e., 2 mg once daily. Alterations to the dose and schedule may be incorporated based on emerging PK, PD, and tolerability data.

Dose reduction and/or truncated dose scheduling may be considered for subjects with recurrent/ persistent toxicity or according to the institutional guideline. For example, once the disease control (CR, CRp, PR or a morphologic leukemia-free state) is attained, ATRA may be given in an intermittent schedule, e.g., 2 week on/2 weeks off.

Subjects may continue treatment in the study until disease progression, unacceptable toxicity, or withdrawal of consent. The duration of study will depend on recruitment rates, and timing of subjects' duration on study. The study will end 2 years from the last subject first dose or earlier if all patients are off study drug. Patients may be allowed to continue on study drug after the end of the study if the Investigator, in consultation with the sponsor's Medical Monitor, determines that continuing treatment will benefit the patient.

Figure 1 Study Schema

- PK/PD expansion: Any dose level could be expanded up to 12 subjects during dose escalation.
- Alternative dosing schedule may be explored.

Protocol waivers or exemptions are not allowed. Therefore, adherence to the study design requirements, including those specified in the Time and Events Table (Section 7.1), are essential.

Supplementary study conduct information not mandated to be present in this protocol is provided in the accompanying Study Procedures Manual (SPM). The SPM will provide the site personnel with administrative and detailed technical information that does not impact subject safety.

4.2. Part 1: Dose-Escalation Phase

4.2.1. GSK2879552 Mono-therapy

In Cohort 1, a single subject will receive a dose of GSK2879552 0.25 mg once daily or the highest dose determined to be safe in FTIH in SCLC study (GSK study 200858), whichever is higher with a maximum of 1 mg/day.

The subject in Cohort 1 will be evaluated for dose limiting toxicities (DLTs) during the first 4 weeks of treatment (DLT observation window), and the safety and PK data will be reviewed prior to a dose escalation decision and starting Cohort 2. If the first subject becomes unevaluable for reasons other than toxicity, another subject will be recruited. The dose-escalation decision and rationale will be documented in writing with copies maintained at each study site and in the master study files at GlaxoSmithKline (GSK).

Starting with Cohort 2, the dose escalation will continue using the Neuenschwander - continuous reassessment method (N-CRM) [Neuenschwander, 2008]. A sufficient number of subjects will be enrolled in each cohort to ensure that data from at least one subject that has completed the DLT observation window is available prior to defining a new dose and starting the next cohort. In addition, subjects who fail to take at least 75% of their scheduled doses in the 4 weeks for reasons other than toxicity will be replaced.

Number of Subjects in a Cohort

The dose escalation will continue with 1 subject per cohort until any of the following events are observed, and then each subsequent cohort will consist of a minimum of 2 subjects.

- Dose limiting toxicity
- Any Grade 2 or higher non-hematologic adverse event that is considered related to the study medication with the following exceptions:
 - Grade \leq 3 fatigue, asthenia, and nausea that respond to standard medical care within 72hrs, significant electrolyte abnormalities unrelated to underlying malignancy and corrected within 24 hrs, and alopecia
- Any grade adverse event that is considered in the judgment of the investigator and GSK Medical Monitor to be serious and related to the drug and requiring additional subjects to better understand the toxicity.

The subsequent cohorts may revert to 1 subject per cohort in either of the following 2 scenarios:

- 2 additional subjects are added at the dose where the toxicity was seen in the initial subject and no additional toxicity meeting the above criteria is seen in either of the 2 new subjects.
- No subjects treated at next higher dose level have toxicity meeting the above criteria.

However, the dose escalation may continue with multiple subjects per cohort per the clinical judgment of the Medical Monitor and internal dose-escalation committee in consultation with the investigators. The decision on the number of subjects will be documented in writing together with the dose escalation decision and the rationale.

Maximum Dose Increment

Built-in safety constraints are in place to prevent exposing subjects to undue risk of toxicity. The dose increment will be no more than 100% of the current dose in the absence of any safety signals. The dose increment will be no more than 50% of the current dose after DLT or any Grade 2 or higher non-hematologic adverse event that is considered related to the study medication (with the exceptions as above) is observed. The maximum allowable dose increment will be determined based on the prior dose level data.

Completion of Dose Escalation

The dose escalation will complete when MTD and/or RP2D is determined. The RP2D will be the MTD or a lower dose that provides adequate PK exposure and biologic activity with superior tolerability. The identification of MTD may not be necessary if a clear RP2D emerges without reaching the MTD. The final determination of RP2D will be based on the N-CRM suggested dose level, or the biologically active dose (e.g., clinical response), the safety profile, and available PK and PD data generated from all subjects in Part 1. Up to 12 additional subjects will be enrolled at the dose to further define the safety and tolerability of the dose and schedule. If necessary, alternate schedules can be explored to determine additional biologically active doses even after a RP2D is defined.

Dose Escalation Committee

An internal dose-escalation committee will be comprised of the following GSK representatives: Medical Monitor, Safety Physician or Scientist, Clinical Scientist, Biostatistician, PK and PD Scientists, and Study Operation Lead. The dose-escalation committee will review available relevant data on demographics, all adverse events including non-DLT toxicities, laboratory assessments, 12-lead ECGs, and dose administration logs, as well as PK data. Quality control of critical safety data will be described in the Dose Escalation Plan, which includes ongoing study monitoring visits, Sponsor review of the clinical database, and confirmation by site investigators and/or delegate that the data is accurate and complete.

On the basis of a review of these data and in joint discussions with the participating investigators, a determination will be made as to whether dose escalation/de-escalation should continue as recommended by the N-CRM. The dose-escalation decision and

rationale for each cohort will be discussed with investigators during teleconference(s) and documented in writing, with copies maintained at each study site and in the study master file.

Description of the Continual Reassessment Method

After each cohort, a dosing recommendation for the next cohort will be made using the N-CRM. All available data, including safety, PK and PD data from current and prior cohorts will be reviewed at the dose escalation meeting. Although the N-CRM will be used to recommend the next dosing level, clinical judgment by the Medical Monitor and internal dose-escalation committee in consultation with the investigators can halt or reduce dose escalation or de-escalate as deemed appropriate at any time during the trial.

The N-CRM design is a type of Bayesian adaptive dose escalation scheme that assumes a two-parameter logistic model for the toxicity rate based on dose. It is a modified version of the original Continual Reassessment Method (CRM) [O'Quigley, 1990]. A CRM-based design uses a statistical model for dose and toxicity, and is expected to locate the MTD efficiently while minimizing the number of subjects exposed to pharmacologically inactive dose levels.

The method is fully adaptive and makes use of all the DLT information available at the time of each dose assignment. In contrast, the 3+3 method only uses information from one dosing cohort at a time.

At the time of each dose escalation decision, the Fixed and Adaptive Clinical Trial Simulator (FACTS, Version 2.3 or higher, Tessella) will be used to obtain, for each potential dose, the posterior probabilities that the DLT rate for that dose lies in each of four toxicity intervals (underdosing, target dose range, excessive toxicity, and unacceptable toxicity). The four DLT toxicity intervals are defined as follows:

- [0%,16%) Underdosing
- [16%, 33%) Target dose range
- [33%, 60%) Excessive toxicity
- [60%, 100%) Unacceptable toxicity

The recommended dose will be the dose with the highest posterior probability of lying in the target dose range with the additional requirement that the sum of the posterior probabilities of the DLT rate lying in the excessive toxicity or unacceptable toxicity range is less than 25%. Selection of the next dose is also subject to the built-in safety constraints of maximum allowed dose increment. An updated estimate of the toxicity curve will be provided at the time of the dose escalation meeting.

Note that de-escalation as well as escalation is possible using this method.

[figure not shown]
Bayesian Prior

The N-CRM methodology requires that a Bayesian prior for the toxicity curve be pre-specified. The Bayesian prior used for this design was determined using the quantile method. For each possible dose, an estimate of the median probability of DLT was specified, along with a 95% credible interval. The 95% credible intervals are intentionally wide due to limited information about the toxicity profile of GSK2879552 in humans. [Table 1](#) shows the median prior probability of experiencing a DLT at a given dose along with a 95% credible interval around the median. This table does not imply that all doses will be studied:

Table 1 Specified Prior Probability of DLT

Dose level (mg)	2.5% Quantile for Probability of Toxicity	Median Probability of Toxicity	97.5% Quantile for Probability of Toxicity
0.25 mg	0.005	0.01	0.2
0.5 mg	0.01	0.02	0.25
1 mg	0.02	0.03	0.3
1.5 mg	0.02	0.04	0.35
2 mg	0.03	0.05	0.4
2.5 mg	0.04	0.06	0.5
3 mg	0.05	0.07	0.6
4 mg	0.05	0.08	0.7
5 mg	0.06	0.1	0.78
6 mg	0.07	0.13	0.85
8 mg	0.08	0.16	0.95
10 mg	0.1	0.2	0.99
12 mg	0.12	0.24	0.99
15 mg	0.13	0.28	0.99
20 mg	0.14	0.35	0.99
25 mg	0.15	0.42	0.99

A graphical presentation of the prior is displayed in the [Figure 2](#). In the figure, the x-axis is natural log (dose/reference dose), where the reference dose is set to 5 mg. Doses are the projected doses. Actual doses used during the conduct of the trial may vary.

Figure 2 Prior Distribution For The Probability of DLT Given Dose**4.2.2. GSK2879552 and ATRA combination**

In Cohort 1, three subjects will receive GSK2879552 2 mg once daily dose with ATRA 45 mg/m²/day as two divided doses. After all three subjects complete the first 4 weeks of treatment, the safety data will be reviewed for DLT. Available PK and PD data will be also reviewed prior to a dose escalation decision and starting Cohort 2. Each cohort will enroll 3 or more subjects to obtain sufficient data. If any subject becomes unevaluable for reasons other than toxicity, a replacement subject will be enrolled. In addition, subjects who fail to take at least 75% of their scheduled doses of each drug in the first 4 weeks for reasons other than toxicity will be replaced. Starting with Cohort1, the dose escalation will use the N-CRM with prior DLT information of GSK2879552 and ATRA monotherapies and follow the same rule with regards to the number of subjects, maximum dose increment, and the completion of dose escalation as described in Section 4.2.1. The details of priors used in N-CRM model is described in Section 13.2.

Starting at dose level 1, the following GSK2879552 dose levels are planned for evaluation in combination with ATRA..

Dose level	GSK2879552	ATRA
1	2 mg/day	45 mg/m ² /day
2	4 mg/day	45 mg/m ² /day
3	8 mg/day	45 mg/m ² /day
4	12 mg/day	45 mg/m ² /day
5	20 mg/day	45 mg/m ² /day

A reduced dose of GSK2879552 or ATRA may be considered if the combination is not well tolerated at dose level 1. The initial dose level reductions allow for either drug to be reduced. Subsequent dose levels are based on the totality of data and upon discussion with the investigators.

Dose level	GSK2879552 ATRA fixed at 45mg/m ²
-1	1 mg/day
-2	0.5 mg/day

Dose level	GSK2879552
	ATRA <30mg/m ²
1a	2 mg/day
-1a	1 mg/day
-2a	0.5 mg/day

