4.2.5. Dose-Limiting Toxicity

An event will be considered a DLT if it occurs within the first 28 days of treatment (with exception of myelosuppression as stated below), and meets one of the following criteria unless it can be clearly established that the event is unrelated to treatment.

Subjects unable to receive at least 75% of scheduled doses within the DLT period for reasons other than toxicity (e.g., acute illness, disease progression) will not be evaluable

- Hematologic DLT: Myelosuppression (as defined by absolute neutrophil count (ANC) $<500/\mu\text{l}$ AND platelets $\leq 25,000/\mu\text{l}$) with bone marrow hypoplasia (cellularity $\leq 5\%$) without evidence of leukemia ($<5\%$ blasts) for ≥ 42 days after drug cessation.
- Grade ≥ 3 non-hematologic toxicity that is considered clinically significant and lasts >72 hours. Fatigue, asthenia, or nausea that respond to standard medical care within 72 hours and new electrolyte disturbance that respond within 24 hours are exceptions. In addition, electrolyte disturbances associated with underlying malignancy are not considered DLT.
- Grade 2 toxicity that in the judgment of the investigator and GSK Medical Monitor is dose-limiting.
- Treatment delay of ≥ 42 days due to unresolved toxicity (without evidence of leukemia ($<5\%$ blasts)).

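### Dose decisions and the MTD outcome close at 28 days, but two DLT criteria can be confirmed only on about Day 43–70, and no rule covers a subject still pending at Day 28

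*Protocol*

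**What the plan says.** **Timing of decisions.** Protocol 4.2.1 sets the monotherapy DLT window as the "first 4 weeks of treatment (DLT observation window), and the safety and PK data will be reviewed prior to a dose escalation decision". From Cohort 2 on, the next dose needs only that "data from at least one subject that has completed the DLT observation window is available prior to defining a new dose". Section 4.2.2 reviews the first combination cohort once its three subjects have finished 4 weeks. SAP Section 2.3 repeats the 4-week window.

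**What counts as a DLT.** Section 4.2.5 begins: "An event will be considered a DLT if it occurs within the first 28 days of treatment (with exception of myelosuppression as stated below"). Two of its four criteria carry their own duration. One is myelosuppression (low neutrophils and low platelets, with a hypoplastic marrow and under 5% blasts) for at least 42 days after drug is stopped. The other is a treatment delay of at least 42 days for unresolved toxicity, again without leukemia. Section 4.2.6 defines the MTD on DLTs in the first 28 days and repeats no exception.

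**Who counts, and what the model sees.** The unevaluable are "Subjects unable to receive at least 75% of scheduled doses within the DLT period for reasons other than toxicity", so a subject held for toxicity stays evaluable. On model input, 4.2.1 says: "The method is fully adaptive and makes use of all the DLT information available at the time of each dose assignment".

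**Brakes.** The increment caps read "The dose increment will be no more than 100% of the current dose in the absence of any safety signals" and "The dose increment will be no more than 50% of the current dose after DLT or any Grade 2 or higher non-hematologic adverse event" (the adverse event must be judged drug-related). The Medical Monitor and committee "can halt or reduce dose escalation or de-escalate as deemed appropriate at any time during the trial". Section 4.8.3 asks for a repeat marrow about 35–42 days after stopping, to look for a hematologic DLT, but ties no cohort decision to it. A Dose Escalation Plan is cited for data quality control; it is not among the documents.

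**The concern.** The definition and the modelled outcome conflict. Section 4.2.5 lets myelosuppression count after Day 28; Section 4.2.6 does not carry that over. The delay criterion has no exception in either place, although it cannot be complete by Day 28.

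The conflict matters because these two criteria are the only routes by which a Grade 4 cytopenia is itself a DLT, and Section 1.4.5.1 names thrombocytopenia as the primary toxicity. A subject whose drug is held for cytopenia at Day 28, with a leukemia-free marrow, is neither a DLT nor clearly DLT-free. The text does not say whether that subject is left out of the N-CRM or entered as no DLT, or whether the next dose waits. At stake is a single wrong step: new subjects started at a dose that the protocol's own overdose limit would exclude a few weeks later.

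**Working it through.** The plan computes no figure on this point, so there is none to reproduce.

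**1. Calendar.** Confirmation day = day of last dose + 42. Last dose on Day 1 gives Day 43; Day 14 gives Day 56; Day 28 gives Day 70. Confirmation therefore falls 43 − 28 = 15 to 70 − 28 = 42 days after the Day 28 review. If the next cohort starts 7 days after the decision (assumed), new subjects could be on the higher dose 8 to 35 days before confirmation.

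**2. One worked decision, monotherapy N-CRM.**
- Model: logit p(d) = α + β·ln(d/5), d in mg; reference dose 5 mg (Section 4.2.1).
- Prior (Appendix 1): α mean −1.6278, SD 1.3652; ln β mean −0.0116, SD 0.4136; correlation 0.2429.
- Rule (Section 4.2.1): choose the dose with the highest P(0.16 ≤ p < 0.33), subject to P(p ≥ 0.33) < 0.25 and the increment cap.
- Data (Table 6): 1 mg 0/1, 2 mg 0/2, 4 mg 0/4, 8 mg 0/1. Add one further 8 mg subject, pending at Day 28. The first 8 mg subject has completed the window, so the condition for the next cohort is met.
- Caps from 8 mg: 100% allows 16 mg (15 mg is the highest listed dose within it); 50% allows 12 mg.

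| Pending subject entered as | 8 mg data | Dose, 100% cap | Dose, 50% cap | P(p ≥ 0.33) at 8 mg | at 12 mg | at 15 mg |
|---|---|---|---|---|---|---|
| Left out | 0/1 | 15 mg | 12 mg | 0.083 | 0.182 | 0.247 |
| No DLT | 0/2 | 15 mg | 12 mg | 0.055 | 0.139 | 0.199 |
| DLT, once confirmed | 1/2 | 6 mg | 6 mg | 0.253 | 0.442 | 0.537 |

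The 50% cap softens the step but does not remove it: 12 mg passes the 0.25 limit before confirmation and fails it clearly afterwards. The fitted prior is not identical to Table 1 (median at 5 mg 0.164 against 0.10), so the table shows direction and size, not an exact forecast.

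**3. Average effect, by simulation.** Appendix 1 true DLT rates; 24 subjects; 10,000 runs; start at 1 mg; cohorts of 1, then 2 after a known DLT; cessation day uniform on 1–28. The share of DLTs that are late is not in the documents; the results below assume 0.25. Columns: wait for every pending subject; open no dose above the pending dose; decide at Day 28 with pending left out; decide at Day 28 with pending coded no DLT.

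| | Full wait | No higher dose | Left out | No DLT |
|---|---|---|---|---|
| Subjects at doses with true rate ≥ 33%: steep | 33.0% | 34.1% | 34.5% | 35.1% |
| moderate | 7.1% | 8.2% | 8.7% | 9.1% |
| shallow | 11.5% | 12.8% | 13.1% | 13.8% |
| Too-toxic MTD chosen: steep | 23.3% | 22.1% | 20.9% | 19.8% |
| moderate | 5.7% | 5.7% | 5.5% | 5.7% |
| shallow | 13.5% | 13.8% | 14.1% | 14.4% |

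Deciding at Day 28 puts 1.5–2.3 points more subjects at too-toxic doses than a full wait (about 0.4–0.6 of a subject in 24), and 0.3–1.0 points more than opening no higher dose. MTD selection does not worsen consistently.

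**4. Frequency.** Section 1.3.5 reports treatment-related Grade 4 thrombocytopenia in 2 of 11 subjects, which is only a precursor. Table 6 shows 0 DLTs in 8 monotherapy subjects; the exact 95% upper limit is 1 − 0.025^(1/8) = 0.37.

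**The case against.** The strongest reply is that the pending state is narrow. The hematologic DLT needs low neutrophils, low platelets, marrow cellularity of at most 5% and under 5% blasts, all sustained for 42 days off drug. Section 1.4.5.1 says hypocellular marrow was generally not seen in animals, and Section 1.3.3 reports platelet recovery by about 4 weeks after dosing. In relapsed or refractory AML few subjects will be clear of leukemia at Day 28, and with blasts above 5% Section 4.8.3 mostly continues dosing. For non-hematologic toxicity, Grade 3 or worse lasting over 72 hours is already a DLT, so the delay criterion will rarely decide. All of this stands; cases are probably uncommon.

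Second, there are brakes. The committee reviews non-DLT toxicities, laboratory data and dosing logs, and can halt. Doubling is allowed only without safety signals, and a held Grade 4 cytopenia may well be one. The simulation models none of this and rests on an assumed late share. That limits its weight, but discretion neither requires a hold nor fixes the model input, and the 12 mg result already applies the tighter cap.

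Third, the worked decision sits near thresholds: 15 mg passes at 0.247 and 8 mg fails at 0.253. The fair contrast is 12 mg against 6 mg, or nearly 8 mg.

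A reader might also infer that the delay criterion can never be met. That is too literal; onset within 28 days is the natural reading, though the text should say so. Nor does it follow that a cohort's only subject, if pending and left out of the model, could support escalation: that strains the requirement for a subject who has completed the window.

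**Conclusion.** The concern holds as a gap in timing and definition. Sections 4.2.1, 4.2.2 and 4.2.6 work to 28 days; two criteria in 4.2.5 cannot be confirmed until about Day 43–70 when drug stops on Day 1–28; the exception in 4.2.5 covers only myelosuppression and is missing from 4.2.6. Nothing in the protocol or SAP says what to do with a pending subject. The unsupplied Dose Escalation Plan might.

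Its size is one wrong step in an occasional cohort: 12 or 15 mg opened where 6 mg would be recommended after confirmation, with P(DLT rate ≥ 33%) at 12 mg moving from 0.14–0.18 to 0.44. That rests on the Appendix 1 prior and the Table 6 data.

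The documents do not support stronger readings: that such cases are common, that many subjects would be overdosed on average, or that the final MTD would be biased. In the steep scenario, deciding at Day 28 chose a too-toxic MTD less often than a full wait. Nothing was computed for the combination arm, whose copula model is not specified; only the timing gap carries over. The change should be made because it is cheap and bears on subject safety.

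**What to change.** 1. In 4.2.5 and 4.2.6, define a DLT as toxicity with onset in the first 28 days, with both 42-day criteria confirmed later and counted in the modelled outcome.
2. In 4.2.1, 4.2.2 and 4.2.5, call pending any subject with under 5% blasts whose drug is held at Day 28 for Grade 4 cytopenia, or for another unresolved toxicity that could still reach the 42-day delay. Never enter that subject in the N-CRM as no DLT while pending, and do not count that subject as the one completed subject that 4.2.1 requires.
3. Open no dose above the pending subject's dose until the toxicity resolves, leukemia is shown, or 42 days have passed since cessation. The same or lower doses may continue.

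The cost is wording in four sections and an occasional delay of up to 42 days to the next higher dose, including for some subjects who then recover. In the simulation at a late share of 0.25, the bar on higher doses added 6–11 days on average to an escalation of about 490–540 days. It added 14–25 days if 10–20% of subjects without a DLT were also pending and recovered (assumed shares). Those figures do not include any further wait from the completed-subject clause in item 2.
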